APPENDIX C

EORTC QLQ-C30 (version 3)

We are interested in some things about you and your health. Please answer all of the questions yourself by circling the number that best applies to you. There are no "right" or "wrong" answers. The information that you provide will remain strictly confidential.

Please fill in your initials:

Your birthdate (Day, Month, Year):

Today's date (Day, Month, Year):

	Not at All	A Little	Quite a Bit	Very Much
1. Do you have any trouble doing strenuous activities, like carrying a heavy shopping bag or a suitcase?	1	2	3	4
2. Do you have any trouble taking a long walk?	1	2	3	4
3. Do you have any trouble taking a short walk outside of the house?	1	2	3	4
4. Do you need to stay in bed or a chair during the day?	1	2	3	4
5. Do you need help with eating, dressing, washing yourself or using the toilet?	1	2	3	4

During the past week:

	Not at All	A Little	Quite a Bit	Very Much
6. Were you limited in doing either your work or other daily activities?	1	2	3	4
7. Were you limited in pursuing your hobbies or other leisure time activities?	1	2	3	4
8. Were you short of breath?	1	2	3	4
9. Have you had pain?	1	2	3	4
10. Did you need to rest?	1	2	3	4
11. Have you had trouble sleeping?	1	2	3	4
12. Have you felt weak?	1	2	3	4
13. Have you lacked appetite?	1	2	3	4
14. Have you felt nauseated?	1	2	3	4
15. Have you vomited?	1	2	3	4
16. Have you been constipated?	1	2	3	4

During the past week:

	Not at All	A Little	Quite a Bit	Very Much
17. Have you had diarrhea?	1	2	3	4
18. Were you tired?	1	2	3	4
19. Did pain interfere with your daily activities?	1	2	3	4
20. Have you had difficulty in concentrating on things, like reading a newspaper or watching television?	1	2	3	4
21. Did you feel tense?	1	2	3	4
22. Did you worry?	1	2	3	4
23. Did you feel irritable?	1	2	3	4
24. Did you feel depressed?	1	2	3	4
25. Have you had difficulty remembering things?	1	2	3	4
26. Has your physical condition or medical treatment interfered with your family life?	1	2	3	4
27. Has your physical condition or medical treatment interfered with your social activities?	1	2	3	4
28. Has your physical condition or medical treatment caused you financial difficulties?	1	2	3	4

For the following questions please circle the number between 1 and 7 that best applies to you

29. How would you rate your overall health during the past week?

A horizontal scale with seven numerical tick marks from 1 to 7. The first tick mark is labeled 'Very poor' and the last tick mark is labeled 'Excellent'.

30. How would you rate your overall quality of life during the past week?

A horizontal scale with seven numerical tick marks (1, 2, 3, 4, 5, 6, 7) and two text labels: 'Very poor' at the left end and 'Excellent' at the right end.

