5.4 Duration of Therapy

In the absence of treatment delays due to adverse events, treatment may continue for a total of 104 weeks in all from the start of study therapy or until one of the following criteria apply:

- Disease progression as defined in Section 7.0
- Inter-current illness that prevents further administration of treatment
- Unacceptable adverse event(s)
- Patient voluntarily withdraws from treatment
- General or specific changes in the patient's condition render the patient unacceptable for further treatment in the judgment of the investigator

Do not hold scans, continue scan schedule every 12 weeks from cycle 5 day 1 regardless of treatment delays thereafter.

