6.0 STUDY PROCEDURES

6.1 SCHEDULE OF ASSESSMENTS:

	Screening (within 28 days)	C1D1	C2D1	C3D1	C4D1	D1C5+	EOT¹²	Follow Up⁸
Informed Consent	X							
Review Eligibility Criteria	X							
Demographics, Height	X							
Prior and Concomitant Medications	X	X	X	X	X	X	X	
Review Adverse Events¹⁰	X	X	X	X	X	X	X	
Physical Examination, Vital Signs¹, Weight	X	X	X	X	X	X	X	
ECOG Performance Status	X	X	X	X	X	X	X	
Survival Status								X Q3m
Laboratory Assessments								
Pregnancy Test for WOBCP²	X							
CBC with diff, platelets³	X	X	X	X	X	X	X	
Comprehensive Metabolic Panel, including Alk Phos⁴	X	X	X	X	X	X	X	

	Screening (within 28 days)	C1D1	C2D1	C3D1	C4D1	D1C5+	EOT ¹²	Follow Up ⁸
LDH	X	X	X	X	X			
PSA¹¹	X	X	X	X	X	X	X	X
Testosterone¹¹	X				X		X	
TSH, free T3, free T4 (If Clinically Indicated: FSH, LH, ACTH)	X	X	X	X	X	X ⁶	X	
Therapy								
Cohorts A and B Nivolumab 3 mg/kg IV q3 wks for up to 4 doses¹³				X				
Cohorts A and B Ipilimumab 1 mg/kg IV q3 wks for up to 4 doses¹³				X				
Cohorts A and B Nivolumab 480 mg IV q4 wks for up to 23 doses¹³						X		
Cohort C Nivolumab 480 mg IV q4 wks¹⁴				X		X		
Imaging Tumor Assessments								
CT chest	X					X (q 12 wks)		
CT Abdomen/Pelvis or MRI Abdomen/Pelvis⁵	X					X (q 12 wks)		
Tc^{99m} Bone Scan (prostate only)	X					X (q 12 wks)		
QoL: BPI-SF and EORTC QLQ C30	X					X (q 12 wks)		
Correlatives								
Tumor Tissue Archival (CRPC preferred if available)	X							
Tumor Biopsy	X						X ⁷	
Research blood⁹		X	X	X		X (q 12 wks)	X	

1. Vital signs will include temperature, pulse, respirations, blood pressure; height will be obtained at screening only.
2. WOCBP: Women of child bearing potential; urine or serum pregnancy test.
3. CBC with diff includes total WBC, hemoglobin, hematocrit and differential of the WBC including absolute counts.
4. COMP or Comprehensive metabolic profile includes sodium, potassium, chloride, bicarbonate, BUN, creatinine, AST, ALT, alkaline phosphatase, total bilirubin.
5. With or without intravenous contrast, before or on associated visit. CT or MRI (preferred) brain with or without IV contrast if suspected or known brain metastases. Frequency of tumor assessments will be q12 weeks.
6. Every 42 calendar days ± 14 business days. May be delayed if infusion is not scheduled within the window.
7. Optional tissue biopsy collection at progression if subject consents; +/- 14 working days.
8. Follow up with phone call or with clinic visit.

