7.1.2 Criteria for PSA Progression

For rising PSA after an initial decline from baseline, the PSA is recorded from the start of therapy to first PSA increase that is \geq 25% and \geq 2ng/mL above the nadir, which is confirmed by a second value 4 or more weeks later, confirming a rising trend. If there is no initial decline from baseline, PSA progression is defined as \geq 25% increase and \geq 2 ng/mL increase from baseline beyond 12 weeks.

Patients who have only documented PSA progression in the absence of radiographic or clinical progression may continue on study therapy.

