7.2 Antitumor Effect- Non-Prostate Malignancies

(For Cohort B only)

For patients with metastatic non-prostate cancer and measurable disease, response and progression will be evaluated using the new international criteria proposed by the Response Evaluation Criteria in Solid Tumors (RECIST) Committee [34]. Changes in only the largest diameter (unidimensional measurement) of the tumor lesions are used in the RECIST v1.1 criteria.

Immunotherapy drugs such as nivolumab and ipilimumab can initially cause inflammation in the early stages of treatment. Immune-related RECIST (irRECIST) utilizes RECISTv1.1 but considers an inflammatory response (or “pseudo-progression”) as normal. The main difference between RECISTv1.1 and irRECIST is that patients can stay on trial after the first progressive disease (PD) assessment (as per RECISTv1.1) if using immune-related

RECIST criteria. This PD per RECISTv1.1 is then re-labeled as immune related stable disease (irSD) per irRECIST and requires addition of unidimensional measurements of all new lesions (that meet the definition of target lesion) to be added to the sum of longest diameters (SLD) calculation for response assessment. Importantly, immune-related progression (irPD) must be confirmed by a follow-up scan at least 4 weeks (within 4-8 weeks) following the initial PD/irSD assessment in order to take the patient off the trial.

Subjects that are deemed to have clinical progression and unstable should not be continued on therapy after PD (per RECISTv1.1) and are therefore not required to have repeat tumor imaging for confirmation as per irPD definition. It is at the discretion of the site investigator whether to continue a subject on study treatment until repeat imaging is obtained. This clinical judgment decision by the site investigator should be based on the subject's overall clinical condition, including performance status, clinical symptoms, and laboratory data.

Treatment Beyond Progression

Accumulating evidence indicates a minority of subjects treated with immunotherapy may derive clinical benefit despite initial evidence of PD.

Subjects treated will be permitted to continue study treatment beyond initial RECISTv1.1 defined PD, assessed by the investigator, as long as they meet the following criteria:

- Investigator determined clinical benefit
- Tolerance of study drug
- Stable performance status

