Quality of Life (QoL) in subjects treated on protocol therapy will be described using EORTC-QLQ-C30 and BPI-SF measures. Baseline will be described using means or medians with an associated variance statistic. Change from baseline will be reported at each time point thereafter with similar descriptive statistics. Each measure will be reported for the overall population and separately by cohort. Each QoL change from baseline will be analyzed using a general linear model with repeated measures for an association with response.

Exploratory Endpoint Analysis

Tumor genome profiling by integrated DNA and RNA sequencing at baseline and optionally at progression will be described using figures representing the profiled patients. These figures will order patients by degree of response (PSA response for Cohort A and Cohort C; and RECIST response for Cohort B). A logistic model with response as the outcome may be used with specific markers as independent covariates to estimate an effect size if a profound pattern is seen. Differences seen in paired samples (baseline and progression) will be described individually and labeled as a responder/non-responder. Immune infiltration in tumor biopsies will be described using figures. Associations of the profiles with the response will be described using counts and proportions.

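### Section 11.3 names a repeated-measures general linear model for quality of life but no rule for missing visits; in its classical form the model would drop every incomplete patient, probably non-responders most

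*Combined protocol and SAP*

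**What the plan says.** - **Analysis (section 11.3, quality-of-life paragraph).** Baseline scores are summarised, and then "Change from baseline will be reported at each time point thereafter with similar descriptive statistics", overall and by cohort. The only inferential step is: "Each QoL change from baseline will be analyzed using a general linear model with repeated measures for an association with response". No estimation method, covariance structure, missing-visit rule, last modelled visit or sensitivity analysis is given.
- **Schedule (section 6.1).** The row "QoL: BPI-SF and EORTC QLQ C30" is marked at screening and every 12 weeks in the column that starts at cycle 5 day 1. It has no mark under end of treatment or follow-up.
- **Cycle lengths (section 6.1, footnotes 13 and 14).** Cohorts A and B have four 21-day cycles and then 28-day cycles. Cohort C has 28-day cycles throughout.
- **Time on treatment (section 5.4).** "treatment may continue for a total of 104 weeks in all from the start of study therapy", unless a stopping criterion applies. One criterion is "Disease progression as defined in Section 7.0".
- **Exceptions.** Section 7.1.2: "Patients who have only documented PSA progression in the absence of radiographic or clinical progression may continue on study therapy". Section 7.2, for Cohort B: "Subjects treated will be permitted to continue study treatment beyond initial RECISTv1.1 defined PD", subject to conditions.
- **Instrument (Appendix C).** The form, including the "For the following questions please circle the number between 1 and 7 that best applies to you" items, shows what is scored. It does not bear on how missing visits are handled.

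**The concern.** The named method is the usual label for repeated-measures ANOVA or MANOVA. In that classical form the visits make up one response vector per patient, and a patient with any element missing leaves the analysis. Nothing in 11.3 tells the analyst to do otherwise.

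The schedule makes this matter. A patient is complete only after staying on treatment for about two years and returning every form. Patients who do not respond are less likely to manage that, and response is the predictor in the model. Two things are at stake:

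- **Precision.** The non-responder group could shrink to a handful, although many of its members had supplied early forms.
- **Bias.** If patients who leave within a response group had a different quality-of-life course from those who stay, the complete cases misrepresent that group.

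**Working it through.** **1. The plan's own figures.** The plan states no number for the quality-of-life analysis, so there is none to reproduce. The response rates used below come from section 11.1 (10% reference and 30% of interest in mCRPC). The Cohort A rule there (15 then 25 patients, continue with 2 or more responses, success with 6 or more) gives

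P(success) = Σ over x ≥ 2 of P(X₁₅ = x) × P(X₁₀ ≥ 6 − x),

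which is 0.802 at 30% and 0.033 at 10%. The plan states 80% power and a 5% type I error, so the figures agree.

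**2. Number of visits.** I read the schedule as a first post-baseline form at cycle 5 day 1, then every 12 weeks up to week 104.
- Cohorts A and B: cycle 5 starts at 4 × 3 = 12 weeks. Forms at weeks 12, 24, 36, 48, 60, 72, 84, 96: 8 visits.
- Cohort C: cycle 5 starts at 4 × 4 = 16 weeks. Forms at weeks 16, 28, 40, 52, 64, 76, 88, 100: 8 visits.

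**3. Complete cases for a common retention r per interval.** The documents give no retention figure, so r is an assumption. It combines staying on treatment and returning the form. The complete fraction is r⁸.

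| r | r⁸ | complete of 65 |
|---|---|---|
| 0.90 | 0.430 | 28 |
| 0.80 | 0.168 | 11 |
| 0.70 | 0.058 | 4 |

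**4. Split by response.** Assume 30% responders in all 65 patients: 19.5 responders and 45.5 non-responders. (Cohort B's target is 25%; using it would give 50 × 0.30 + 15 × 0.25 = 18.75 responders, a small change.)

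| group | r (assumed) | all 8 visits | at least one visit |
|---|---|---|---|
| responders | 0.90 | 19.5 × 0.430 = 8.4 | 19.5 × 0.90 = 17.6 |
| non-responders, low | 0.65 | 45.5 × 0.65⁸ = 45.5 × 0.0319 = 1.4 | 45.5 × 0.65 = 29.6 |
| non-responders, higher | 0.80 | 45.5 × 0.80⁸ = 45.5 × 0.168 = 7.6 | 45.5 × 0.80 = 36.4 |

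Under constant attrition the median time on treatment is 12 × ln 0.5 / ln r weeks: 19.3 weeks (about 4.4 months) at 0.65 and 37.3 weeks (about 8.6 months) at 0.80.

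**5. Second check, by time on treatment.** Take Cohort A at the 10% reference rate: 25 × 0.9 = 22.5 non-responders. With exponential time on treatment and median w weeks (months × 52.18/12), complete cases = 22.5 × 0.5^(96/w), and patients with at least one visit = 22.5 × 0.5^(12/w). If 90% of forms are returned per visit, multiply the complete cases by 0.9⁸ = 0.43.

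| assumed median, months | complete, all forms returned | complete, 90% returned | at least one visit |
|---|---|---|---|
| 3 | 0.1 | 0.1 | 11.9 |
| 6 | 1.8 | 0.8 | 16.4 |
| 9 | 4.1 | 1.8 | 18.2 |
| 12 | 6.3 | 2.7 | 19.2 |
| 18 | 9.6 | 4.1 | 20.2 |
| 24 | 11.9 | 5.1 | 20.8 |

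The last column takes the first form as returned. Even at 12 months with every form returned, complete cases are 6.3 of the 19.2 non-responders that an all-visit model would keep, about one third.

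**The case against.** The strongest reply is that 11.3 does not prescribe listwise deletion. The same phrase is also used for repeated-measures linear models fitted by likelihood to all observed visits, and nothing says that all 8 visits must enter one model. This stands: a reader might infer that the plan commits the sponsor to complete cases, and the documents do not say so. They also do not say the opposite, and the classical reading is a natural one.

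A reader might also infer that almost no non-responder would remain. That holds only under assumed short treatment, a median of roughly 6 months or less. Non-response is also not the same as leaving treatment. PSA-only progression does not require stopping, Cohort B may continue past a first RECIST progression, and a patient with stable disease is a non-responder who has not progressed. This stands too, and it is why a range is given.

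A third inference would be that early forms go unused. They do not: the per-visit descriptive summaries carry no complete-case restriction. Only the association model is exposed.

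Finally, quality of life is a secondary endpoint, and this model has no hypothesis, power or decision rule attached. That limits the weight of the point, but it does not supply the missing rule.

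**Conclusion.** The model in 11.3 is under-specified in a way that could matter. Run in its classical form, it would exclude every patient with a missing visit on an 8-visit, on-treatment schedule where missing forms are likely to be related to the predictor.

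Under the assumptions shown (30% responders, 90% of them retained per interval), about 8 responders would be complete. Complete non-responders would be 1.4 of 45.5 at 65% retention, or 7.6 at 80%, against about 30 or 36 kept by a model using all available visits. These sizes rest on assumed retention, constant over time, because the documents give none. They are conditional on listwise deletion, which the documents neither state nor rule out.

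The effect is confined to one secondary association analysis. The response-rate decisions are untouched.

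**What to change.** Replace the model sentence in section 11.3 with:

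> For each QoL score, change from baseline will be modelled by a linear mixed model for repeated measures, fitted by REML to all available post-baseline visits, with no patient excluded for a missing visit. Fixed effects are visit number, response, response-by-visit and cohort; the within-patient covariance is first-order autoregressive. The last visit modelled will be fixed before the analysis, and later visits will be described only. Form completion will be reported by visit and response.

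Visit number is used because the calendar weeks differ between Cohort C and Cohorts A and B. One covariance is named and the last visit is fixed in advance, so that neither is chosen after seeing the data.

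The cost is wording only: the same forms, patients and schedule. If the sponsor already intended a likelihood fit, the change only records it. The model relies on data being missing at random. That is weaker than what a complete-case analysis needs, but it can still fail, since no form is collected at end of treatment. The completion table lets a reader judge this. Because response is itself a post-baseline outcome, the result remains an association and should be reported as one.

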3.1 Inclusion Criteria

- 3.1.1 Age \geq 18 years and ability to understand and the willingness to sign a written informed consent.
- 3.1.2 ECOG Performance Status of 0, 1 or 2.
- 3.1.3 Subjects must have histologic or cytologic or radiologic evidence of metastatic adenocarcinoma of the prostate without small cell histology OR another type of metastatic carcinoma. Radiologic or pathologic evidence of metastases is allowed.
- 3.1.4 All subjects, regardless of cancer type, must have a documented CDK12 loss on a CLIA approved, Next Generation Sequencing assay (tissue, cell-free DNA or other is allowed) and is willing to provide archival tissue for analysis. CDK12 loss will be confirmed by the IND Sponsor (at the University of Michigan) and may include deleterious mutations (e.g truncating mutation, inactivating missense mutation), rearrangement or deletion. Because it is not always stated explicitly in all NGS platforms/assays, the Sponsor Investigator will determine which genomic aberrations constitute CDK12 loss. If tissue is unavailable, subject may still enroll.
- 3.1.5 Subjects with prostate cancer must have documented prostate cancer progression within six months prior to screening with PSA progression defined as a minimum of two rising PSA levels ≥ 1 ; at least one week between each assessment with a baseline PSA value at screening of ≥ 2 ng/mL, including after first generation anti-androgen withdrawal.
- 3.1.6 Subjects with prostate cancer must have ongoing androgen deprivation with total serum testosterone < 50 ng/dL (or < 0.50 ng/mL or 1.73 nmol/L). If the subject is currently being treated with LHRH agonists (subjects who have not undergone an orchiectomy), this therapy must have been initiated at least 4 weeks prior to registration. This treatment must be continued throughout the study.
- 3.1.7 Subjects with non-prostate histologies must have RECIST 1.1-measurable cancer on computed tomography (CT) or magnetic resonance imaging (MRI) scans.
- 3.1.8 Subjects must have recovered to baseline or \leq grade 1 CTCAE v 4.03 from toxicities related to any prior treatments unless AE(s) are clinically non-significant and/or stable.
- 3.1.9 Patients must be ≥ 2 weeks from most recent systemic therapy or most recent radiation therapy.
- 3.1.10 Women of childbearing potential must have a negative serum or urine pregnancy test within 28 days prior to registration. Women of non-childbearing potential are

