5.0 TREATMENT PLAN

5.1 Treatment Dosage and Administration

Protocol treatment must start within 14 business days of enrollment to the study.

- 5.1.1 In this study, Cohort A and Cohort B patients will start treatment with nivolumab dosed at 3 mg/kg IV and ipilimumab 1 mg/kg every 3 weeks for up to 4 doses. Cohort C patients will receive immunotherapy with nivolumab dosed at a flat dose of 480 mg IV every 4 weeks for up to 26 doses or 104 weeks.
- 5.1.2. Cohorts A and B maintenance immunotherapy with nivolumab dosed at a flat dose of 480 mg IV every 4 weeks will be continued for up to 23 doses or 92 weeks. Missed doses of 480 mg Nivolumab due to toxicity or general health condition will be skipped.

5.1.3 Total protocol therapy for all Cohorts will be up to 104 weeks during treatment. If disease progression or recurrence occurs during the follow-up phase, then per treating physician discretion, the patient may resume nivolumab 480 mg IV every 4 weeks until progression if tolerated with axial imaging as per protocol every, 12 weeks.

5.1.4 All study therapy will be administered on an outpatient basis.

Agent	Precautions	Dose	Route	Schedule	Cycle Length
Nivolumab (solution for injection) induction Cohort A and B only	Administer before other immunotherapy agents	3 mg/kg up to 4 doses	IV infusion over 30 minutes, +/- 10 minutes, with a sterile, nonpyrogenic, low protein binding 0.2 to 1.2 micrometer in-line filter. Follow with saline flush.	Day 1	3 weeks
Ipilimumab (solution for injection) induction Cohort A and B only	Administer 30 minutes after nivolumab.	1 mg/kg up to 4 doses	IV infusion over 90 minutes, +/- 10 minutes, through a non-pyrogenic, low protein-binding in-line filter. Separate IV line required.	Day 1	3 weeks
Nivolumab (solution for injection) maintenance After induction in Cohorts A and B; and throughout in Cohort C	Administer before other immunotherapy agents	480 mg up to 23 doses (92 weeks in Cohort A and B, and 104 weeks in Cohort C)	IV infusion over 30 minutes, +/- 10 minutes, with a sterile, nonpyrogenic, low protein binding 0.2 to 1.2 micrometer in-line filter. Follow with saline flush.	Day 1	4 weeks

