APPENDIX B

Brief Pain Inventory (Short Form)

STUDY ID #: _____

DO NOT WRITE ABOVE THIS LINE

HOSPITAL #: _____

Brief Pain Inventory (Short Form)

Date: _____ / _____ / _____

Time: -----

Name: _____

First

[figure not shown]
Middle Initial

1. Throughout our lives, most of us have had pain from time to time (such as minor headaches, sprains, and toothaches). Have you had pain other than these everyday kinds of pain today?

1. Yes

2. No

2. On the diagram, shade in the areas where you feel pain. Put an X on the area that hurts the most.

3. Please rate your pain by circling the one number that best describes your pain at its worst in the last 24 hours.

4. Please rate your pain by circling the one number that best describes your pain at its least in the last 24 hours.

0 1 2 3 4 5 6 7 8 9 10
No Pain Pain as bad as
Pain you can imagine

5. Please rate your pain by circling the one number that best describes your pain on the average.

A horizontal scale from 0 to 10. The numbers 0, 1, 2, 3, 4, 5, 6, 7, 8, 9, and 10 are evenly spaced along the top. Below the scale, the text "No Pain" is centered above the number 0, and the text "Pain as bad as you can imagine" is centered above the number 10.

6. Please rate your pain by circling the one number that tells how much pain you have right now.

A horizontal scale from 0 to 10. The numbers 0, 1, 2, 3, 4, 5, 6, 7, 8, 9, and 10 are evenly spaced along the top. Below the scale, the text "No Pain" is centered under the number 0, and the text "Pain as bad as you can imagine" is centered under the number 10.

STUDY ID #: _____ DO NOT WRITE ABOVE THIS LINE HOSPITAL #: _____

Date: _____ / _____ / _____
Name: _____

Time: _____

Last

First

Middle Initial

7. What treatments or medications are you receiving for your pain?

8. In the last 24 hours, how much relief have pain treatments or medications provided? Please circle the one percentage that most shows how much relief you have received.

0% 10% 20% 30% 40% 50% 60% 70% 80% 90% 100%
No Relief Complete Relief

9. Circle the one number that describes how, during the past 24 hours, pain has interfered with your:

A. General Activity

0 1 2 3 4 5 6 7 8 9 10
Does not Interfere Completely Interferes

B. Mood

0 1 2 3 4 5 6 7 8 9 10
Does not Interfere Completely Interferes

C. Walking Ability

0 1 2 3 4 5 6 7 8 9 10
Does not Interfere Completely Interferes

D. Normal Work (includes both work outside the home and housework)

0 1 2 3 4 5 6 7 8 9 10

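### The only QLQ-C30 and BPI-SF before treatment is the screening form, so change between screening and first dose is counted in the QoL change from baseline

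*Combined protocol and SAP*

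**What the plan says.** In the Section 6.1 schedule, the row "QoL: BPI-SF and EORTC QLQ C30" is marked under the column "Screening (within 28 days"), is blank from C1D1 to C4D1, and resumes every 12 weeks from D1C5+. The same table marks ECOG status, weight, CBC, metabolic panel, LDH and PSA (footnoted to Cohort A) at C1D1.

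Section 11.3 describes QoL at baseline and then states: "Change from baseline will be reported at each time point thereafter with similar descriptive statistics". It also models each change score for an association with response. It does not say which form is the baseline.

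Recall periods are set by the instruments. In Appendix C, QLQ-C30 items 6 to 28 sit under a past-week heading, and the two global items state it themselves: "29. How would you rate your overall health during the past week". Items 1 to 5 have no recall period. In Appendix B most BPI-SF items cover 24 hours: "9. Circle the one number that describes how, during the past 24 hours, pain has interfered with your". The average-pain and current-pain items do not.

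Four other provisions bear on timing:
- Section 3.1.9 requires at least "2 weeks from most recent systemic therapy or most recent radiation therapy".
- Section 3.1.8 requires recovery from earlier toxicity to baseline or grade 1, but exempts events that are stable or of no clinical importance.
- Section 5.1: "Protocol treatment must start within 14 business days of enrollment to the study".
- Section 5.3 bars chemotherapy, biological therapy and radiation during screening as well as treatment.

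**The concern.** A change score is only as good as its starting value. Here that value is taken at an unspecified point in a four-week window. It describes the week (QLQ-C30) or day (BPI-SF) before that point, and it is not repeated before dosing. Two things can move QoL between the form and the first infusion: recovery from the previous treatment, and worsening of the disease (Section 3.1.5 requires documented progression in the prostate patients). Recovery would read as improvement on study, and worsening as harm. No cohort has a control group to absorb either, and QoL is a named secondary objective and endpoint (2.2.4, 2.5.4).

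**Working it through.** The plan gives no figure on this point to reproduce. The check is calendar arithmetic followed by a decomposition of the change score.

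**1. Age of the baseline form at first dose.** Section 6.1 does not say what the 28 days count back from.
- Counted to first dose: at most 28 days. Section 7.3 uses this anchor for baseline tumor measurements, which may be no more than 4 weeks before treatment begins.
- Counted to enrollment, with treatment starting 14 business days later: 14 business days are 18 or 20 calendar days depending on the weekday (no holidays), so 28 + 18 = 46 to 28 + 20 = 48 days. Section 3.1.10 counts the pregnancy test, which sits in the same Screening column, back from registration.

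The documents do not settle which applies to QoL.

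**2. Overlap of the recall period with prior therapy.** Read Section 5.3 strictly, so that the form must follow the last prior therapy. Let *d* be the number of days from the last therapy day to the form, and take the recall period as the 7 days before the form. Recall days on or before the last therapy day = 8 − *d* for *d* = 1 to 7, and 0 from *d* = 8.
- Example with last therapy on day −14: a form on day −13 has 7 − 0 = 7 such days (8 − 1), a form on day −7 has 1 (8 − 7), and a form on day −6 has none.
- For the 24-hour BPI-SF items there is overlap only at *d* = 1.

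Sections 3.1.8 and 5.3 make overlap less likely. Neither fixes when in screening the form is completed.

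**3. Next form.** At C5D1 the time since first dose is 4 × 21 = 84 days in Cohorts A and B, and 4 × 28 = 112 days in Cohort C if C5D1 is read in 28-day cycles. No QoL value lies between screening and that visit.

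**4. What this does to the estimates.** Let S be the screening score, B the score just before the first infusion (not collected) and Y the score at a later visit.
- Reported change: Y − S = (Y − B) + (B − S).
- Cohort mean: mean(Y − S) = mean change since first dose + δ, where δ = mean(B − S). More patients shrink the standard error but not δ.
- Responders versus non-responders: the contrast in reported change equals the contrast since first dose plus (δ_R − δ_NR). If drift is the same in both groups, this extra term is zero.

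The documents give no SD for QoL, no expected change and no distribution of washout times, so δ has no computable value or sign.

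**The case against.** A reader might infer that the baseline can be taken while the patient is still on chemotherapy or radiation. The washout alone would allow it: with last therapy on day −14, a form on any of days −28 to −13 (16 of 28) has its whole recall week on or before the last therapy day. But 15 of those days (−28 to −14) place the form on or before a day of treatment that Section 5.3 bars during screening. That reading is not protocol-compliant. What remains is the 1-to-7-day overlap for QLQ-C30 items 6 to 30, and almost none for the BPI-SF.

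A reader might also infer that every planned QoL result is biased one-for-one. Step 4 shows that this is true of the mean changes but not of the response model.

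Three further points can be made for the plan:
- QoL is a descriptive secondary endpoint with no hypothesis, threshold or decision rule. This stands and limits the importance.
- Recovery from prior therapy may continue after C1D1, and an uncontrolled cohort cannot attribute QoL change to the drug from either baseline. This also stands. A C1D1 form removes only the part of the drift that precedes dosing, but that part is avoidable.
- The questionnaires are standard and their wording is not at fault. Agreed: the gap lies in the Section 6.1 schedule combined with the Section 11.3 analysis.

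**Conclusion.** The concern holds in a limited form. Followed exactly, the plan puts up to 28 days of change before first dose into the descriptive mean QoL changes (46 to 48 days only under the enrollment reading and the latest permitted start). It leaves no way to separate that change afterwards. The association with response is affected only if drift differs by response.

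It is tempting to put a size on the bias. If one assumed an SD of change of 20 to 25 points, 25 patients would give a 95% half-width of 1.96 × 20/√25 = 7.8 to 1.96 × 25/√25 = 9.8 points, and an assumed mean drift of 5 to 10 points would be 5/9.8 = 0.5 to 10/7.8 = 1.3 times that. The documents support none of these inputs. The upper ratio pairs the largest drift with the smallest SD, opposite drifts may offset each other, and not all 25 patients need reach C5D1. Size and direction should be treated as unknown.

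PSA response, the go/no-go rules, sample size and power are untouched. This is a cheap improvement, not a flaw in the main result.

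**What to change.** In Section 6.1, mark both questionnaires at C1D1 and state that they are completed before the first infusion. The explicit wording is needed because the general window of ±3 business days under the schedule would otherwise admit a form filled in after dosing.

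In Section 11.3, define QoL baseline as the last form completed before first dose, with the screening form as fallback if the C1D1 form is missing. For patients already enrolled, use the screening form and report its age in days at first dose.

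The cost is one short set of questionnaires at an existing visit. Moving the mark instead of adding one costs no extra form but gives up the fallback. Patients never dosed are replaced under Section 5.8, so no change score is lost. The remaining downside is mixed baseline timing between patients enrolled before and after the change, which the reported form age makes visible. Sample size and power do not change.
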